Background: One in ten Veterans seen in Veterans Health Administration (VHA) primary care clinics has PTSD. Individuals with PTSD are more likely to report impairments in physical functioning, including health-related limitations in climbing stairs or performing common household tasks. As an essential component of overall functioning and quality of life, physical functioning is an independent predictor of risk for adverse health outcomes, including mortality. Mechanisms underlying the association of PTSD and poor physical functioning are multifactorial, but a key contributing factor is likely persistent low levels of physical activity. Barriers to engaging in physical activity may include low perceived behavioral control for making positive long-term lifestyle changes and personal attitudes about the harms (vs. benefits) of physical activity. Those with PTSD have reduced self-efficacy for behavioral change and less ability to cope with setbacks, leading to greater difficulty with initiating and maintaining new health behaviors. Individuals with PTSD are also more likely to have ongoing pain and fatigue, which may contribute to beliefs about harmful effects of physical activity and lead to avoidance of activity. Current VHA outpatient programs are primarily focused on addressing physical activity in the context of specific medical conditions (eg, obesity or cardiovascular disease), and there is a paucity of programs specifically tailored to the unique needs of Veterans with PTSD. Development of effective programs to increase physical activity for Veterans with PTSD may therefore improve their physical functioning and represent an important contribution to VHA efforts to enhance health and recovery for this population.

Objectives/Aims: The overall objectives of this study are to develop and pilot test a novel intervention aimed at initiating and maintaining higher levels of physical activity for Veterans with PTSD.

Aim 1: Adapt graded exercise therapy (GET) and incorporate motivational interviewing and mHealth to increase physical activity and improve physical functioning for Veterans with PTSD.

Aim 2: Conduct a pilot study to examine feasibility and acceptability of the intervention for a future randomized controlled trial.

Methods. To increase physical activity for Veterans with PTSD, this project will combine GET, motivational interviewing, and mobile health technology (mHealth) to address attitudinal and behavioral barriers particularly relevant for this group. First, we will work collaboratively with our Veteran Engagement Panel to adapt GET protocols effective for non-PTSD populations (eg, adults with chronic pain or fatigue), and incorporate motivational interviewing and mHealth. We will then pilot test the intervention in 3 consecutive groups of 6-8 participants (total n=18-24) and use concurrent mixed-methods to examine feasibility and acceptability. Quantitative measures will include recruitment (proportion enrolled out of total eligible); attendance (proportion who attend 75% of in-person visits); and retention (proportion who complete data collection post-intervention). Qualitative assessments will involve semi-structured interviews on acceptability of

intervention components (eg, session formats and topics, usability of mHealth), and barriers and facilitators to attendance. At baseline, during and post-intervention, we will also assess overall and physical functioning using Veterans RAND 36-item, 6-minute walk, and 30-second sit to stand, and collect additional data (PTSD symptoms, depression, pain, fatigue, and sleep quality) to inform a future randomized trial.

List of Abbreviations

CCDOR.....	Center for Care Delivery & Outcomes Research
CBT	Cognitive Behavioral Therapy
Co-I.....	Co-Investigator
ED.....	Emergency Department
GET	Graded Exercise Therapy
HSRD	Health Services Research and Development
IRB.....	Institutional Review Board
mHealth	Mobile Health Technology
MVAHCS	Minneapolis VA Health Care System
NIH	National Institutes of Health
PACT	Patient Aligned Care Team (VA primary care staff)
PCMHI	Primary Care Mental Health Integration
PCL-5	PTSD symptom checklist for the DSM-5
PC-PTSD-5.....	Primary Care Screen for PTSD for DSM-5
PEG	Brief 3-item Scale on Pain Intensity & Interference
PHQ-9.....	Patient Health Questionnaire-9
PI	Principal Investigator
PSQI	Pittsburgh Sleep Quality Index
PTSD	Posttraumatic Stress Disorder
PT.....	Physical Therapist
RR&D	Rehabilitation Research and Development
UMN	University of Minnesota
VA.....	Department of Veterans Affairs
VHA	Veterans Health Administration
VINCI.....	VA Informatics and Computing Infrastructure
VR-36	Veterans RAND 36-item Health Questionnaire
WRAP.....	Wearables Research and Analytics Platform

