Our Engagement Panel is adapted from a previously developed model of patient engagement,^{49, 50} and is comprised of 12 Veterans who have lived-experience with PTSD, including 6 men and 6 women of diverse race and ethnicity, 25-67 years old. The panel meets quarterly and more often, as requested to support ongoing projects. Meetings of 2-3 hours are organized by the CCDOR Engagement Workgroup, with input from project teams on topics and goals. Meetings begin with a brief investigator presentation on overall project goals and 2-3 key questions for panel members to address. Workgroup staff facilitate meetings, take detailed notes during meetings and review themes with project teams immediately afterwards. Investigators are also provided written summaries of key feedback. Co-Investigator [name] will lead collaboration with the Veteran Engagement Panel on session formats and topics (eg, additional barriers to address), communication materials (eg, brochures and worksheets for activity planning), and recruitment procedures.

3. Adaptation of GET and integration with motivational interviewing

We will combine GET and motivational interviewing in individual meetings and group sessions to be delivered by a trained PT.

At the first individual meeting, participants will complete in-person baseline assessments, learn about intervention rationale and components, discuss their values and goals, describe preferences for types of physical activity (eg, walking), and be introduced to mHealth components. Weekly group sessions in month 1 will involve closed cohorts of 6-8 participants and be conducted by video-conferencing (see Section 4b below). Based on our experience with motivational interviewing, chronic pain rehabilitation, and PTSD psychotherapies, the group format should optimize development of relationships and support between participants, while also permitting personalized attention to motivations and barriers. Additionally, groups may be particularly beneficial for individuals with PTSD, who are often isolated and have greater difficulty making

The proposed 4-month intervention will focus on initiation (months 1-2) and maintenance (months 3-4) of higher physical activity levels (Figure 2). In month 1, sessions will employ GET and motivational interviewing to provide intensive, personalized counseling, thereby over-coming barriers to initiation. In month 2, further gains in physical activity will be supported by

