RTI will provide weekly data to the VA study team, and once obtained, these data will be stored behind the VA firewall (see section below on protection of participant privacy for full description of information security procedures). VA study staff may review participants' physical activity and sleep data via the company website, in order to provide feedback to participants on their progress. RTI will also assist with generating weekly activity summary progress reports for participants. These will include physical activity data to provide updates on participants' progress towards their activity goals (eg, minutes of walking or biking per day). The reports may display physical activity data using graphs and other figures available through the device company accounts (see Appendix 1). Additionally, reports will include messages of encouragement that are tailored to the participants' progress that week (Table 3). Finally, we will provide a short summary statement of financial incentives they should expect (eg, "You met your goals on 3 days during this past week. This means you will receive \$6."). In all communications with RTI (and materials sent by them), participants will be referred to by their dummy email & device identifier. RTI will not have access to any identifiable participant information.

Table 3. Examples of Tailored Messages

Group 1: Meeting daily activity goals \geq 5 days per week	Group 2: Meeting daily activity goals 3-4 days per week	Group 3: Meeting daily activity goals 0-2 days per week
You are on the right track!	. You will be on your way to a healthier new you!	New activities can be challenging to do. Take it one day at a time!
You are on your way to a healthier new you!	We know this is tough but keep at it!	We know it is not easy, but it is worth it! Tell a friend what you look forward to most!

b. Video-conferencing

Due to the COVID-19 pandemic and higher risk for group activities, we will conduct all group sessions and some individual meetings (see Appendix 2) via videoconferencing on Zoom, a VA and HIPAA compliant videoconferencing platform. VA ORD permits group meetings via platforms that are approved by the ISSO. Zoom is included in the VA Technical Reference Model (TRM), a list of VA-approved technologies. We will audio-record some sessions to assess intervention fidelity.

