We propose to conduct a pilot study of 3 groups with 6-8 participants each (total n=18-24). Based on our clinical and research experience with piloting group interventions, and number of participants in the active arm of recent pilot studies of group exercise interventions for PTSD,^{25, 26} we expect that 3 groups will provide sufficient data on feasibility and acceptability to inform a larger study. A control group will not be enrolled as examining efficacy is not appropriate at this stage,^{53, 54} and our main goal is to evaluate feasibility and acceptability of the active intervention. Co-Investigator [name] will be the PT interventionist conducting in-person assessments, video-conferencing sessions, and telephone calls. We will use a concurrent mixed-methods approach to assess feasibility and acceptability, and anticipate making protocol modifications as appropriate. Data on physical activity, functioning, and symptoms will also be collected, to determine feasibility of outcomes assessments for a future randomized trial.

1. Human Subjects Involvement & Characteristics.

We will screen Veterans being seen in-person or having virtual care appointments at MVAHCS primary care clinics for PTSD (ie, ≥3 on Primary Care Screen for PTSD-5) and self-reported health-related limitations in mobility (ie, climbing several flights of stairs or walking several blocks). Exclusion criteria include ongoing suicidal ideation or psychosis; medical contraindications to exercise (eg, complete paraplegia); high degree of disability (ie, impairments in ≥2 basic activities of daily living); plans to move out of the area permanently within 4 months; major neurocognitive impairment (eg, dementia), schizophrenia; acute mental health crisis within the past 3 months (requiring an ED visit or hospitalization); and routinely completing 150 minutes or more of moderate to vigorous activity per week. We will not recruit prisoners, institutionalized individuals, or children. Our goal is to conduct 3 groups of 6-8 participants each (18-24 total).

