The study coordinator will schedule a telephone call with Veterans to go over the informed consent form, HIPAA authorization form, and enrollment forms for financial incentives. We will also include other materials to describe the study (eg, FAQ document, expectations for confidentiality and privacy during group meetings, and troubleshooting Zoom). We will mail potential participants these materials ahead of the phone call, instructing them not to sign any forms until the call. During the call, the study coordinator will provide a thorough overview of study participation, risks, benefits, alternatives, protections, and IRB and study staff contact information. We will emphasize the voluntary nature of study participation and provide the opportunity for questions about the study. The consent process will be conducted by the study coordinator, who is trained in the ethics of human subject research. Those who agree to participate will mail back signed informed consent and HIPAA authorization forms via prepaid stamped envelopes. Signed informed consent and HIPAA authorization forms will be received by the study team before collection of any participant data.

5. Quantitative Data & Analyses (Table 4)

Feasibility will be quantitatively assessed as **recruitment** (proportion enrolled out of total identified as eligible), **attendance** (proportion who attend $\geq 75\%$ of in-person visits), and **retention** (proportion who complete post-intervention assessments). To determine feasibility, we will first evaluate recruitment and time needed to enroll participants. We anticipate approximately

20 Veterans per month may be eligible (based on preliminary data noted above), and with 20% recruitment, we expect to complete enrollment for each group in 4-6 weeks. We have set attendance and retention benchmarks at 75%, which are realistic estimates based on recent pilot studies of group exercise interventions for PTSD (participants attended an average of 78-82% of sessions and overall retention were 76-82%).^{25, 26}

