Data on participant **physical activity** will be collected using both wearable devices and self-reported activity dairies. **Physical functioning** will be measured at baseline and post-intervention using VR-36, 6-minute walk,^{58, 59} and 30-second sit to stand.^{59, 60} Based on our clinical experience, these latter 2 tests can be feasibly administered to detect small but clinically relevant improvements in endurance and lower body strength. We will also assess **PTSD symptoms** (PTSD Checklist for DSM-5 [PCL-5])^{61, 62}; **depression** (Patient Health Questionnaire-9 [PHQ-9])⁶³; **pain** (brief 3-item scale on intensity and interference [PEG])⁶⁴; **fatigue** (PROMIS 4-item short form)⁶⁵; **sleep quality** (PROMIS sleep disturbance and impairment)^{66, 67}; **self-efficacy** (PROMIS general 4-item⁶⁸ and one item specific to physical activity); and **social support** for physical activity (1 item). We will compare physical activity data from wearable devices and self-reported diaries, for consistency and data quality for these different methods. For measures of physical functioning, PTSD and other symptoms, we will refine procedures for administering assessments and also confirm consistency and data quality.

Table 4. Assessments during Pilot Study.

	Baseline	During Intervention	Post-intervention
Feasibility & Acceptability			
Recruitment, Attendance & Retention		X	X
Acceptability of intervention components (semi-structured interviews)		X	X
Barriers & facilitators to attendance (semi-structured interviews)		X	
Physical Activity & Functioning			
Wearable device physical activity & sleep data		X	
Self-reported physical activity diaries	X	X	X
VR-36, 6-minute walk, 30-second sit to stand	X		X
Medical Conditions & Symptoms			
Medical diagnoses, medications (EMR)	X		
PTSD symptoms (PCL-5)	X		X
Depressive symptoms (PHQ-8)			
Pain (PEG)	X		X
Fatigue (PROMIS 4-item)	X		X
Sleep Disturbance & Impairment (PROMIS)	X		X
Self-efficacy	X		X
Social support for physical activity	X		X
EMR=Electronic Medical Record; PCL-5=PTSD Checklist for DSM-5; PEG=3-item scale on pain intensity and interference; PHQ-9=Patient Health Questionnaire-9; PROMIS=Patient Reported Outcomes Measurement Information System; PSQI=Pittsburgh Sleep Quality Index; VR-36=Veterans RAND 36 Item Health Survey			

6. Qualitative Data & Analyses (Table 4)

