Qualitative assessments will involve semi-structured interviews at the end of month 2 and post-intervention, to address **acceptability** of intervention components, including session formats and topics and usability of wearable devices. Month 2 interviews will also elicit **barriers and facilitators** to attendance. Interviews will be audiorecorded and transcribed. We will use triangulation to integrate qualitative interview data with quantitative measures of attendance and retention. First, Drs. [name] and [name] will apply an established rapid approach for qualitative analysis to identify key themes.⁶⁹ This involves reviewing transcripts for the initial 3-4 interviews to develop templates that are then applied to summarizing subsequent transcripts. Summary information will be further reviewed and analyzed using matrices to identify major themes for each main topic (eg, acceptability of mHealth components). Then, a matrix will be

developed to compare themes for those who attended 75% of in-person visits with those who did not. A similar matrix will compare themes for those who completed post-intervention assessments and those who did not.

7. Withdrawal of Subjects

Participants can withdraw from the study at any point in time and for any reason by contacting study personnel in person, by telephone, or by mail, and requesting to withdraw. We anticipate termination of participation if:

1. The participant becomes ineligible to participate
2. The participant does not follow instructions from the researchers
3. The study is unexpectedly suspended or canceled.

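### Attendance is scored on in-person visits, but all 11 numbered intervention sessions are virtual, so none of them counts and attendance nearly repeats retention

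*Combined protocol and SAP*

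**What the plan says.** Feasibility has three quantitative measures: recruitment, attendance and retention. The last two carry a 75% benchmark (section 5.0 C.5).

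- **Attendance.** The Methods summary gives "attendance (proportion who attend 75% of in-person visits". Section 5.0 C.5 repeats this with an at-least sign. Section 5.0 C.6 uses the same split for a qualitative matrix, comparing "those who attended 75% of in-person visits with those who did not".
- **Retention.** Section 5.0 C.5 gives "proportion who complete post-intervention assessments".
- **Basis of the benchmark.** Section 5.0 C.5 cites earlier pilots in which "participants attended an average of 78-82% of sessions and overall retention were 76-82" percent.
- **Delivery.** Section 5.0 B.3 says "Weekly group sessions in month 1 will involve closed cohorts of 6-8 participants and be conducted by video-conferencing". Section 5.0 B.4.b says that, because of COVID-19, "we will conduct all group sessions and some individual meetings" by video. Section 5.0 C describes the interventionist as "conducting in-person assessments, video-conferencing sessions, and telephone calls", which treats in-person contact as something separate from video and phone.
- **Schedule.** Appendix 2 states the mode of each contact it lists. Only the week 0 baseline visit and the week 16 final assessment are labelled in person.

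**The concern.** A feasibility pilot of a mostly remote programme needs to show whether people take part in the remote sessions. The attendance rule counts only visits made in person, and Appendix 2 places those visits before the first group session and at the end of the 16 weeks.

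Two things are at stake. First, two of the three quantitative feasibility measures, and both of those with a benchmark, would carry almost the same information, and no prespecified quantitative measure would describe uptake of the sessions. Second, section 5.0 C.6 plans one matrix by attendance and another by completion of the final assessments. If the two groupings nearly coincide, the month 2 interview themes on barriers to attendance are sorted by who returned at week 16 and not by who attended sessions.

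**Working it through.** **Contacts by mode (Appendix 2)**

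| Contact | Weeks | Number | Mode |
|---|---|---|---|
| Baseline visit | 0 | 1 | In person |
| Tech prep call | 0.5 | 1 | Zoom |
| Group sessions 1-4 | 1, 2, 3, 4 | 4 | Zoom |
| Individual sessions 1-3 | 1.5, 2.5, 4.5 | 3 | Phone |
| Individual sessions 4-7 | 5-8 | 4 | Phone |
| Final assessment | 16 | 1 | In person |

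In-person visits: 1 + 1 = 2. Numbered intervention sessions: 4 + 3 + 4 = 11, all virtual. The tech prep call is left out because it is not a numbered session; including it gives 12 virtual contacts.

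The two 75% figures (the per-person threshold and the benchmark) are set by the authors and not derived, so there is no calculation of theirs to reproduce.

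**Visits needed under the current rule.** Visits needed = 0.75 × number of visits, rounded up. With 2 visits, 0.75 × 2 = 1.5, so 2 are needed; one of two is 50% and fails. Among participants with a baseline visit, the rule is therefore met exactly when the week 16 visit is attended. If 75%, 76% or 82% of them attend that visit, attendance is 75%, 76% or 82%.

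**If interviews count as visits.** Section 5.0 C.6 does not give the mode of the interviews.
- Month 2 interview in person: 0.75 × 3 = 2.25, so 3 of 3.
- Both interviews as separate in-person visits: 0.75 × 4 = 3, so 3 of 4.

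In either case 0 of the 11 sessions enter the count.

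**Two participants under the current rule**

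| | Sessions joined | Week 0 | Week 16 | Classified as |
|---|---|---|---|---|
| A | 0 of 11 | Yes | Yes | Attender |
| B | 11 of 11 | Yes | No | Non-attender |

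**How much the replacement denominator matters.** Take *p*, the mean share of sessions attended, as 0.78 to 0.82 (section 5.0 C.5). A 75% threshold means 0.75 × 4 = 3 of 4 group sessions, or 0.75 × 11 = 8.25, so 9 of 11 group and individual sessions. With independent sessions the share passing is a binomial tail; at *p* = 0.80:

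- At least 3 of 4: 4(0.8³)(0.2) + 0.8⁴ = 0.4096 + 0.4096 = 0.819.
- At least 9 of 11: 55(0.8⁹)(0.2²) + 11(0.8¹⁰)(0.2) + 0.8¹¹ = 0.295 + 0.236 + 0.086 = 0.617.

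To allow for some people attending more consistently than others, I used a beta-binomial with within-person correlation ρ, parameters *p*(1/ρ − 1) and (1 − *p*)(1/ρ − 1). The ρ values are assumptions.

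| ρ | At least 3 of 4, *p* = 0.78 / 0.80 / 0.82 | At least 9 of 11, *p* = 0.78 / 0.80 / 0.82 |
|---|---|---|
| 0 | 0.788 / 0.819 / 0.849 | 0.551 / 0.617 / 0.684 |
| 0.3 | 0.750 / 0.775 / 0.800 | 0.628 / 0.662 / 0.697 |
| 0.5 | 0.749 / 0.773 / 0.796 | 0.673 / 0.701 / 0.730 |

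The 75% benchmark sits at the bottom edge of the first range (about 75-85%) and above all of the second (about 55-73%).

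**The case against.** The best reply is that the intended measure can be guessed. Group sessions moved to video because of the pandemic, so the phrase may be left over from a face-to-face design. The benchmark is argued from sessions attended, and the month 2 interviews ask about barriers to attendance. A sensible team might simply count sessions. This is also a single-arm pilot of 18-24 people with no hypothesis test and no go/no-go rule tied to the benchmark, and the team expects to modify the protocol as it goes.

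The inference about leftover wording is reasonable, but the documents do not say it. The same phrase appears in all three places, and section 5.0 C separates in-person contact from video and phone, so the text does not readily stretch to cover Zoom. If the team counts sessions anyway, the denominator is unstated, and choosing it after seeing the data could decide whether the benchmark is met.

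Four smaller points stand in part:

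- The baseline visit has intervention content, including 20 minutes of motivational interviewing, and Table 2 lists it as an individual meeting. Some intervention contact is therefore counted. But everyone with baseline data attended it, so it does not separate attenders from non-attenders.
- Attendance and retention are not identical. They can differ if final assessments are completed remotely, if someone comes at week 16 without completing them, or if an interview counts as an in-person visit.
- Table 4 is weak support. It marks "Recruitment, Attendance & Retention" during and after the intervention, but the row combines three measures, so the marks cannot be assigned to attendance alone.
- The pass-rate comparison applies a figure from group exercise pilots to short phone calls as well. It shows that a denominator must be named; it does not measure the harm done by the current wording.

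**Conclusion.** The concern holds, and the definition must be corrected before enrolment. Followed as written, the rule counts 0 of 11 numbered intervention sessions and requires 2 of 2 in-person visits. Among those with a baseline visit it gives nearly the same answer as retention. It also does not measure what its benchmark rests on, the share of sessions attended.

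The count of 0 of 11 rests on the modes stated in Appendix 2 and holds whether or not interviews are in person. The near-duplication of retention rests on the final assessments being done at the week 16 visit, as Appendix 2 schedules them. Only the pass-rate ranges depend on outside assumptions: that mean attendance would match the cited 78-82%, and that within-person correlation lies between 0 and 0.5.

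**What to change.** 1. In the Methods summary and sections 5.0 C.5 and C.6, define attendance on scheduled intervention sessions in place of in-person visits.
2. Fix one denominator before enrolment, for example at least 3 of 4 group sessions or at least 9 of 11 group and individual sessions, and state that the 75% benchmark applies to it. Which to choose is a design decision, but the benchmark should be reconsidered alongside it, since the two options give different expected pass rates.
3. Report the mean percentage of sessions attended as well, because that is the form of the pilot figure cited.
4. Use the week 16 visit for retention only, and use the new attendance definition in the qualitative matrix.
5. State the mode of the interviews and that they do not count toward attendance.

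The cost is a wording change in three places and a record of attendance at each scheduled session. The documents do not describe session logs, so it is an assumption that this recording is easy. No extra participants or visits are needed.
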